## **Abstract**

*Background:* Depression is a common comorbidity with chronic illness. Previous studies on depression treatment in these populations have not focused on bright light therapy (BLT) for non-seasonal depression. Patients diagnosed with cystic fibrosis (CF) and chronic obstructive pulmonary disease (COPD) can under-report depressive symptoms under the assumption that they are an expected part of the disease process. Symptoms of depression can lead to increased episodes of disease exacerbation and hospitalizations.

*Methods:* Four adult patients with an existing diagnosis of either CF or COPD were assigned to the intervention of BLT 30 minutes daily for a goal of seven consecutive days. The primary outcome observed was depressive symptom changes recorded by subjective completion of Beck's Depression Inventory II (BDI-II) pre-intervention and post-intervention. The secondary outcome was compliance with daily bright light therapy documented via daily logs by the bedside nurses.

*Results:* There was not a significant improvement in depressive symptoms pre-intervention versus post-intervention among both populations ( $p=0.196$ ). There was no significant correlation found between number of compliant days with changes in BDI-II scores pre- and post-intervention ( $p=0.213$ ). There were no adverse events to be reported with this trial.

*Conclusion:* BLT is a well-tolerated intervention for the hospitalized adult CF and COPD population. Larger-scaled studies with a control group may be useful in the future for establishing validity behind this intervention.

*Limitations:* Limitations include a small sample size, inconsistency with daily compliance, and factors surrounding completion of this study during the COVID-19 pandemic.

*ClinicalTrials.gov Identifier:* NCT04921332

*Keywords:* cystic fibrosis; chronic obstructive pulmonary disease; depressive symptoms; chronic illness; affect; bright light therapy

## **1. Background**

Depression in chronic illnesses such as CF and COPD often goes undetected, undiagnosed, and untreated (American Lung Association, 2021b). Many patients suffering from chronic illnesses simply assume that depressive symptoms are just a normal part of the disease process, especially in multifactorial disease such as CF and COPD (American Lung Association, 2021b; Cystic Fibrosis Foundation, 2020). Previous studies have not always observed a chronically ill and frequently hospitalized population. Additionally, most studies have only observed the effects of BLT on seasonal depressive disorders rather than nonseasonal. Focused studies with the CF or chronically ill populations have been limited by small sample sizes.

Complex and chronic respiratory illnesses encompass a variety of diagnoses, including CF and COPD. Quittner et al. (2014) examined the presence of depression and anxiety symptoms among CF patients and their caregivers and found that 29% of adult CF patients had a positive screening on the Center for Epidemiologic Studies Depression Scale (CES-D) ( $p < 0.001$ ). Unmanaged depression among patients with CF can result in the individual being less likely to manage his or her treatment plan, exhibit poor lung function, have a lower body mass index, higher health care costs, an increased number of hospitalizations, and an overall decrease in his or her quality of life (Cystic Fibrosis Foundation, 2020). COPD is characterized by long-term disability, early mortality, and currently has no definitive cure (American Lung Association, 2021). Approximately one-third of patients diagnosed with COPD experience symptoms of either anxiety or depression (Griffith et al, 2020). Patients with COPD and major depressive disorder have a 43% increased risk of multiple adverse COPD outcomes, which may include more frequent disease exacerbations, new anxiety or depression events, and increased mortality (Marsh & Guck, 2016).

Treatment with daily BLT is known as a first-line therapy for seasonal depression (Campbell, Miller, & Woesner, 2017). To expand its usage studies investigating the application of BLT in non-seasonal depression found improvement in non-seasonal depressive symptoms when applying BLT to multiple populations which included inpatients with major depressive disorder (MDD) and hospitalized CF patients (Guzel Ozdemir et al. 2015; Kopp et al. 2015; Lam et al. 2016). BLT is overall well-tolerated, affordable, and effective (Yorguner Kupeli et al., 2018). Although BLT can take two weeks or more to reach its maximum effect, symptoms can start to improve within a few days of consistent use (Mayo Clinic Staff, 2017).

The purpose of this project was to apply a daily 30-minute BLT intervention to adult CF or COPD patients hospitalized for acute pulmonary infection or exacerbation to decrease symptoms of depression as measured subjectively by depression inventory scoring. The primary research question being investigated is whether a BLT intervention would be effective in reducing depressive symptoms among hospitalized adult CF and COPD patients.

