### *2.1 Sample*

This study took place on the pulmonary step-down and transplant unit at a 1,600-bed academic medical facility in Southwestern Pennsylvania. Recruitment occurred after the nurse clinician in the pulmonary stepdown unit spoke with the patient and asked if they were comfortable discussing the study with the principal investigator (PI).

Inclusion criteria were adult patients 18 years of age and older with an existing diagnosis of either CF or COPD. The BDI-II survey was administered following a waiver to written consent and only patients with a score of  $>/= 14$  or mild depression symptoms were invited to participate. This minimum score was determined in order to be high enough to allow visible changes in depression symptoms following a seven day intervention. Demographics including diagnosis, education level, ethnicity, and age were recorded for each participant (Table 1).

Exclusion criteria included patients who had pre-existing ophthalmological conditions or photosensitivity due to the use of a bright light; migraines because the bright light could be a trigger; those receiving high dose steroids for transplant rejection due to potential for mood altering qualities; those receiving certain antibiotics that increased light sensitivity; those with bipolar disorder because light therapy may trigger mania; and admissions anticipated to span less than 48 hours because this would not be a long enough span for therapy to produce a visible effect on depressive symptoms. Children were excluded because only adult CF and COPD subjects are admitted to this hospital and unit. This study only consisted of one admission period for the inpatient. If the patient were to be readmitted, potential for bias from previous exposure existed; therefore, re-enrollment was not offered.

The initial target number of patients for this study was 30. With the primary interest being in feasibility and acceptability of this intervention, this study will assist in providing support for a larger-scaled study; therefore, a sample size of 30 is appropriate for these purposes. No power analysis was performed for this study.

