### *2.2 Study Design*

This was a quasi-experimental, pre- and post- intervention, single group study. No control group was utilized for comparison. A single bright light lamp was assigned to each individual patient throughout the duration of the intervention.

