Since participants with a history of bipolar mood disorder were excluded from this study, the 15-item "Mood Disorder Questionnaire" was administered manually from a printed paper survey during the pre-screening process to determine history of bipolar disorder symptomatology since this was not able to be determined solely based on medical chart review (Hirschfield, 2006). Basic demographic data including age, disease diagnosis, ethnicity, and education level was manually collected from each participant via a checklist completed by the PI (Table 1). At this time, a random identifying code was assigned to the participant for confidentiality. Bright light therapy began the morning following enrollment. The lamp was placed in a position approximately 16-24 inches from the subject's face by the principal investigator initially. Proper positioning of the lamp was included in bedside nurse education in order to ensure that it was placed correctly before being turned on each morning. A small reference sheet and disposable measuring tape was attached to each lamp to ensure continued proper use and distance from the patient. A preliminary 10-minute session of bright light therapy (BLT) was initiated following consent in order to ensure no acute reactions or sensitivities were experienced from the light. The brightness level was set at 10,000 lux. If the participant experienced sensitivity or adverse effects during this pretest time, which may have included eyestrain, headache, nausea, or irritability, therapy began at 2,500 lux the following day and gradually increased by 2,500 lux per day as tolerated by the patient. The PI was responsible for adjusting this setting in these instances. Color temperature was set to warm white (3,500K), medium white (4,250k), or daylight (5,000k) for the duration of the study depending on the participant's preference during pretesting. The participant was able to request that this be changed during the study when the PI would be present for routine monitoring. The PI also provided contact information to the participant and nursing staff so that she could be reached if needed. These settings were automatically saved when the lamp was turned off making it easy to maintain the same settings for seven days of therapy. The lamp stayed in the subject's room until the seven-day goal was completed or the patient was discharged or transferred. The bedside registered nurse turned on the lamp and set the timer upon entering the room in the morning when the patient would awaken. The automatic timer on the lamp turned off therapy after 30 minutes. The bedside nurse would initial a log documenting the day and time therapy was initiated and whether it was initiated on that day. The PI was responsible for routinely monitoring participants and following up on whether there were disruptions in therapies during each session (this was not the bedside nurse's responsibility). Disruptions may have included the patient self-discontinuing therapy for that day or leaving the

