#### **4. Discussion**

The primary outcome of this study was the mean scoring of the BDI-II pre- and post-intervention had a reduction; however, this reduction was not statistically significant based on the yielded p-value. It is fair to consider whether a seven day intervention period is long enough to produce a change in pre- and post-BDI-II scores. It is also difficult to differentiate internal factors that may have altered the subjective scores for patients. There are many other factors that could impact depressive symptoms aside from bright light therapy especially in a complex and chronically ill patient. A drawback of this intervention is that the trigger of score changes would be virtually impossible to differentiate as bright light therapy or other external or internal factors, such as changes in the participant's prognosis, hospital discharge plan, or personal life. This would also make clinical significance of this intervention difficult to decipher.

The secondary outcome of compliance data was recorded as a "Y" or "N" for each individual day across the seven-day intervention period. Among subjects, there was inconsistency with both the number of days of consecutive treatment. Following statistical evaluation using a chi-square test, there was no association between days of compliance and changes in BDI-II scores pre- and post-intervention.

Depression symptoms continue to be prevalent among the chronically and complex ill population. Such pathology is associated with increased general hospitalization risk, longer length of hospital stays, and an elevated risk of readmission (Prina et al., 2015). The average length of stay among the participants in this study was 31.25 days. The average cost of a general hospital stay per day, not specifically for complex respiratory disease management, is \$2,607 (Fay, 2021). Considering this information, reducing depressive symptoms can have not only a subjective impact on depressive symptoms, but also an impact on subject quality of life as well as a financial impact secondary to the additional cost per hospital day caused by increased lengths of hospital stays and readmission rates. Future studies may be useful in examining these factors as secondary outcomes.

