#### **5. Limitations**

This study had several limitations. According to [name], the primary CF physician at UPMC Presbyterian, the recent use of the medication Trikafta ® for CF is reducing the number of hospitalizations among this patient population. This new therapy has recently been FDA approved and has shown in two clinical trials to improve components of pulmonary function (U.S. Food and Drug Administration, 2019). This decreased the potential candidate pool on the inpatient unit. This reduction in candidate availability resulted in the COPD population being included approximately halfway through the data collection period.

The limited availability of nursing staff also impacted this study. Oftentimes, the principal investigator would have difficulty locating the usual caregiver to approach the patient and ask permission to speak with him or her. There was additional difficulty with nursing staff consistently offering bright light therapy to enrolled patients daily. As an attempt to improve the consistency of applying the intervention, education was provided to the staff during monthly staff meetings prior to study initiation and at the halfway point. Despite this additional training, the staff had trouble initiating the intervention due to altered workloads and staffing due to the COVID-19 pandemic.

This study occurred during the COVID-19 pandemic. Some patients were apprehensive about having an extra, unnecessary individual in their room. Many patients were encouraged to avoid hospitalization if possible, during the COVID-19 pandemic. Only one site and one patient care unit were used for recruitment.

It was also challenging for participants to complete the 30-minute bright light therapy sessions due to needing to complete off unit testing and treatment requirements. The patients on this particular unit are still acutely ill and being actively treated while hospitalized. Many are dependent on hemodialysis scheduled early in the mornings, diagnostic procedures, and surgical procedures. This decreased the likelihood that bright light therapy would be completed consistently for those particular days.

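### The primary question is whether BLT works, but an uncontrolled pre-post change in BDI-II cannot answer it, and Section 2.1 names a different primary aim (feasibility and acceptability)

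*Combined protocol and SAP*

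**What the plan says.** Section 1 (Background) states the primary research question as "whether a BLT intervention would be effective in reducing depressive symptoms among hospitalized adult CF and COPD patients". The Abstract names change in BDI-II as the primary outcome, and Section 2.5 analyses it with a paired t-test at a two-sided 0.05 level.

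Section 2.2 describes the design: "This was a quasi-experimental, pre- and post- intervention, single group study. No control group was utilized for comparison". Section 2.3 gives no untreated interval: "Bright light therapy began the morning following enrollment". Section 1 describes the target patients as "hospitalized for acute pulmonary infection or exacerbation", and Section 5 adds: "The patients on this particular unit are still acutely ill and being actively treated while hospitalized". Entry requires a BDI-II of 14 or more, for this reason: "This minimum score was determined in order to be high enough to allow visible changes in depression symptoms following a seven day intervention". Section 5 says the study was not blinded, and the outcome is self-reported. Section 2.3 allows the repeat score to be taken by telephone after discharge.

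Two other statements bear on the point. The sample-size paragraph of Section 2.1 says the main interest is feasibility and acceptability, in support of a larger study, and that no power analysis was done. The Discussion accepts that "the trigger of score changes would be virtually impossible to differentiate as bright light therapy or other external or internal factors".

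**The concern.** A paired test asks whether the total change is zero. The primary question asks whether light changed the score. These coincide only if scores would have stayed level without light, and nothing in the documents supports that. The patients were in hospital, under treatment, chosen for a raised score on the outcome scale, and aware that they were receiving the intervention.

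The stated primary question therefore has no estimate. A significant fall would not show that light works. The non-significant result does not show that it fails. Recruiting more patients to the same design would narrow the interval around the wrong quantity.

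**Working it through.** **Inputs (Tables 4 and 5).** Mean fall 8.750, SD of change 10.563, n = 4. Target N = 30 (Section 2.1). Entry floor 14 (Section 2.1).

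**1. Reproducing the reported result.** SE = 10.563/√4 = 5.28. t = 8.75/5.28 = 1.657 on 3 df, two-sided p = 0.196. The 95% CI is 8.75 ± 3.182 × 5.28, or -8.06 to 25.56. This agrees with the tables to rounding, so the arithmetic is sound. The problem is what it estimates.

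**2. What the change contains.** Write D = L + B, where D is the total fall, L the part due to light and B everything else. The design observes D only. The documents give neither the size nor the sign of B. With assumed values of B:

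- B = +5 (improvement without light): L = 8.75 - 5 = 3.75, interval -13.06 to 20.56.
- B = 0: L = 8.75, interval -8.06 to 25.56.
- B = -5 (worsening without light): L = 8.75 + 5 = 13.75, interval -3.06 to 30.56.

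**3. The test at the planned size when light does nothing (L = 0).** The chance of a significant result comes from the noncentral t with 29 df and noncentrality B√30/SD. B and the two smaller SDs are assumptions.

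| SD of change | B = 0 | B = 3 | B = 5 | B = 8.75 |
|---|---|---|---|---|
| 10.563 (observed) | 0.05 | 0.325 | 0.707 | 0.992 |
| 8 | 0.05 | 0.51 | 0.911 | 1.00 |
| 6 | 0.05 | 0.754 | 0.993 | 1.00 |

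The converse also holds. If light lowered scores by 5 points while illness raised them by 5, D would be zero and the test would be significant only 5% of the time. At N = 30 and SD 10.563 the 95% half-width is about 3.9 points, but B stays in the estimate.

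**4. One component of B: regression to the mean.** The documents describe no second score before light, so I take the screening score as the baseline. For an unselected normal score with mean μ, SD s and retest correlation r, let a = (14 - μ)/s. The expected fall without any treatment is (1 - r) × s × φ(a)/(1 - Φ(a)). All three inputs are assumptions, ranging over μ 10 to 15, s 8 to 10 and r 0.6 to 0.9.

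- Smallest (μ = 15, s = 8, r = 0.9): 0.6 points.
- Largest (μ = 10, s = 10, r = 0.6): 4.3 points.

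**5. The two stated aims side by side.** Section 1 and the Abstract make symptom change primary, read as effectiveness. Section 2.1 makes feasibility and acceptability the main interest. A single group can serve the second aim but not the first.

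**The case against.** The strongest reply is that this is a small feasibility study that says so. Section 2.2 states that there is no control group, the Discussion concedes that attribution is not possible, and Section 5 admits participant bias. The Abstract concludes only that light was well tolerated, and it refers validity to larger controlled studies. All of that stands, and no false claim of efficacy was made. It does not settle the matter. Section 1 still poses effectiveness as the primary question, and a significance test is still its reported answer. Neither the Abstract's limitations nor Section 5 lists the missing comparator.

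A reader might infer three stronger points that the documents do not support.

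- **That recovery, attention and discharge planning all push scores down, so 8.75 overstates the light effect.** The direction is not documented. Section 5 calls the patients still acutely ill, Section 3.1 mentions intensive care transfers, and the Section 2.1 inclusion criteria do not require an acute episode. Attention from daily lamp sessions was also uneven, since two of the four patients had only two or three days of light.
- **That stays of 14 to 55 days left room for a randomised delayed start.** Those are total admission lengths in four completers, not days remaining after enrolment. Eligibility excludes only anticipated stays under 48 hours, and 8 of the 20 screened patients who were not enrolled failed even that.
- **That one patient's dominance measures the bias.** With whole-number scores and the floor of 14, Tables 4 and 5 fit only 36 to 12, 28 to 24, 18 to 11 and 17 to 17. One patient thus supplies 24 of the 35 points (69%). That shows fragility at n = 4. It does not size the effect of lacking a control, and a controlled study this small would be just as fragile.

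**Conclusion.** The concern holds as a mismatch between question and design. The primary analysis estimates total change during a hospital stay with BLT. It does not estimate the effect of BLT, whatever its p-value. The mismatch is compounded by Sections 1 and 2.1 disagreeing on the primary aim.

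The size of the bias cannot be derived from the documents. The illustrative range is wide: a true null would be declared significant at N = 30 between 32.5% and 99.3% of the time for an assumed background improvement of 3 to 5 points and an SD of 6 to 10.563. Regression to the mean alone could plausibly contribute 0.6 to 4.3 points under the stated assumptions. The core conclusion needs none of these figures. It rests on the absence of any comparator and on the Discussion's own concession. Because the limitation is largely disclosed and the published conclusion is modest, the remedy is a matter of objectives and reporting.

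**What to change.** 1. Reconcile Section 1 with Section 2.1 by making feasibility and acceptability the primary objective, measured by enrolment, days of light delivered and completion of the repeat BDI-II. The documents already hold figures for this, such as 7 + 6 + 2 + 3 = 18 of 28 intended days of light (64%).
2. Restate the BDI-II aim as describing the change during a hospital stay with BLT. Report the mean change with its 95% CI (8.75, -8.06 to 25.56, n = 4), not as a test of effectiveness.
3. Reword the Abstract's sentence on the lack of significant improvement, and the Discussion's opening sentence on the primary outcome, to match.
4. Add the absent comparator to the limitations in the Abstract and in Section 5.

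This costs wording only. The downside is that the study no longer claims to test effectiveness.

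A randomised delayed start is an option for a later study, not a repair for this one. At 15 v 15 with SD 10.563, SE = 10.563 × √(2/15) = 3.86, the 95% half-width is about 7.9 points and power is about 24% for a 5-point difference. With an assumed SD of 8 those last two figures are 6.0 and 38%; with 6 they are 4.5 and 60%. The observed SD rests on four patients (95% interval roughly 6 to 39, assuming normality). An unblinded wait would also leave expectation and attention in the comparison.
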